7.4	Definition of Adverse Events.....	47
7.5	Reporting Procedures	48
	Reporting of Non-Serious Adverse Events (NSAE).....	48
	Reporting of Serious Adverse Events (SAE)	49
7.5.3	Reporting of Unexpected Serious Adverse Events/Problems (USAE/SUSAR)	49
7.6	Follow-up for Adverse Events	50

7.7	Safety Monitoring	50
7.7.1	Adjudication of Adverse Events	51 8
INTERVENTION	DISCONTINUATION	51 9
	STATISTICAL CONSIDERATIONS	52
9.1	General Design Issues	52
9.2	Sample Size and Randomization	53
9.2.1	Treatment Assignment Procedures	54
9.3	Interim analyses and Stopping Rules	55
9.4	Outcomes	55
9.5	Data Analyses	56
10	DATA COLLECTION AND QUALITY ASSURANCE	57
10.1	Data Collection Forms (eCRFs)	57
10.2	Data Management	57
10.3	Quality Assurance	58
10.3.1	Training	58
10.3.2	Protocol Deviations	59
10.3.3	Monitoring	59
11	PARTICIPANT RIGHTS AND CONFIDENTIALITY	60
11.1	Institutional Review Board (IRB) Review	60
11.2	Informed Consent Forms	60
11.3	Participant Confidentiality	61
11.3.1	Protection while data being collected	62
11.4	Study Discontinuation	62
12	ETHICAL CONSIDERATIONS	63
12.1	Declaration of Helsinki	63
12.2	Ethics/IRB Committee	63
12.3	Subject Information and Consent	63

12.4	Subject Data Protection.....	64
12.5	Compensation for Injury	64
12.6	Conflict of Interest	64
12.7	Registration of Study and Disclosure of Study Results	65
13	COMMITTEES	65
	PUBLICATION OF RESEARCH FINDINGS	14
		65
15	REFERENCES	66
16	SIGNED AGREEMENT OF THE STUDY PROTOCOL	71
17	APPENDICES:	72

- I. Schedule of Assessments
- II. Screening Log
- III. Study Drug Accountability Record
- IV. Protocol Deviation Log
- V. Primary Medical Doctor Letter
- VI. Delegation of Authority Log
- VII. Subject Code List

PRECIS

Study Title

Statin Neuroprotection and Carotid Endarterectomy: Safety, Feasibility and Outcome (STANCE)

Objectives

The purpose of this study is to evaluate the safety, feasibility and outcome of administering three different statins at submaximal and maximal dose on early cognitive dysfunction (eCD) and delayed cognitive dysfunction (dCD). The primary study objectives are to:

- 1) Determine whether patients on a pre-existing sub-maximal dose of the three most commonly prescribed statins (simvastatin <40mg, atorvastatin <80mg, rosuvastatin

- <20mg) experience a higher incidence of eCD and dCD than those randomized to 218 doses of pre-operative statin supplementation to the maximal dose (simvastatin 40 mg, atorvastatin 80 mg, rosuvastatin 20 mg).
- 2) Determine whether approximately 2-18 doses of optimal statin supplementation is sufficient by comparing whether patients randomized to receiving statin supplementation each individually experience a higher incidence of eCD and dCD than those patients on a pre-existing maximal dose of the three most common statins, and whether statins that pass the blood-brain barrier better correlate with reduced eCD and dCD.
 - 3) Determine whether patients on no pre-existing statin regimen exhibit less eCD and dCD when randomized to 2-18 doses of pre-operative maximal dose atorvastatin (80mg) compared to minimum dose atorvastatin 10mg.
 - 4) Determine a dose-response relationship to these 3 statins by determining whether all patients at the time of surgery have less eCD and dCD if they are on: 1) simvastatin 40mg rather than on <40mg; 2) atorvastatin 80mg rather than on <80mg; and 3) rosuvastatin 20mg rather than on <20mg.

The secondary study objectives are to:

- 1) Determine whether a pre-operative statin regimen alters the prevalence of early mortality at Day 365 +/- 30.
- 2) Determine whether differences in eCD/dCD identified in Primary Objectives 1- 4 are associated with either:
 - a. levels of, or peri-operative changes in, ESR/CRP, and/or
 - b. changes in either activities of daily living (BLESSED) or cognition (TICS-M) in the year following randomization and surgery.

Design and Outcomes

This is a phase III study for patients with carotid artery stenosis designed to assess if maximizing statin doses for (2-18) prior to carotid endarterectomy (CEA) is neuroprotective. All patients undergoing this procedure and who can tolerate the statin regimen will be asked to participate in this multi-center study. If patients are already on a statin, then only patients on *atorvastatin*, *simvastatin*, or *rosuvastatin* will be recruited. Subject participants will be grouped to one of three arms as a function of their pre-existing statin regimen, or lack thereof. Throughout the term of the study, subject participants will be closely monitored for medication compliance as well tolerance and safety via phone calls and in person.

The randomization will be stratified by center, previous use of statin and in random blocks of 4 and 6.

We have defined our primary outcome on Z-scores based on the mean and standard deviation of cognitive testing change in scores of a surgical reference group before and after surgery (24h and approximately 30 days post-op OR when the patient returns for their post-CEA clinical visit). The cognitive testing was divided by cognitive domains and the patients were considered to have postoperative early cognitive dysfunction (eCD) based on two criteria to account for

both focal and global/ hemispheric deficits. Consequently, anyone with: (a) ≥ 2 SD worse than reference group in two or more cognitive domains or (b) ≥ 1.5 SD worse than the reference group in all cognitive domains tested will be considered a primary outcome. If the subjects experience stroke or TIA peri-operatively, they will be considered as having reached a secondary outcome in the study.

Interventions and Duration

Participant subjects who are already on the maximal statin dose of either atorvastatin (80 mg), simvastatin (40 mg or 20 mg + amlodipine) or rosuvastatin (20 mg) will remain on their current statin doses and will be part of our observational arm (ARM 1). The subjects that are currently on sub-maximal daily doses of the previously mentioned statins will be randomized to their current dose plus placebo or their current dose plus the necessary milligrams needed to bring them to the FDA approved maximal dose per day for their corresponding statin (ARM 2). Those subjects who are statin naïve, 30 days prior to enrollment, will be randomized to daily doses of either 10 mg of atorvastatin or 80 mg of atorvastatin (ARM 3).

We will stay in contact with the subjects via phone calls prior and post their CEA to assure study drug compliance and safety. We will also assess them prior to their CEA, 12-25 hours post-CEA for early cognitive dysfunction (eCD) and during their post-operative clinical visit (approximately at 30 days post-CEA) for delayed cognitive dysfunction (dCD). The final follow-up phone call will be one year after their CEA procedure.

Sample Size and Population

One thousand CEA patients, who fulfill the remaining inclusion criteria, will be enrolled in the study prior to their scheduled CEA. We will enroll these patients at various sites over a 5 year period in one of our three study arms. We estimate that we will assign: 225 participants who are already on maximal daily doses of one of the study statins (atorvastatin 80 mg or simvastatin 40 mg or rosuvastatin 20 mg) to the Observational Arm (ARM 1). We will randomize 675 participants that are on sub-maximal doses of statins to either remain at their current dose or be increased to the FDA approved maximal daily dose of their current statin (ARM 2). We will randomize 100 participants that are statin naïve to receive a daily dose of either 10 mg of atorvastatin or 80 mg of atorvastatin.

The reported expectations for this study have been delineated based on our past experience studying carotid endarterectomy patients. We expect pregnant women and women with childbearing potential will not be included in this study. The average age of our patient population is 72, and hence most female patients are well beyond their reproductive age.

PARTICIPATING STUDY SITES

1. **Columbia University Medical Center**, Dept. of Neurological Surgery, [name] and ColumbiaDoctors Midtown, [name].

2. **Albany Medical College/Vascular Group at Albany**, [name]
3. **State University of New York at Buffalo**, [name]
4. **Valley Hospital**, [name]
5. **Baylor College of Medicine**, [name]
6. **University of Alabama at Birmingham**, [name]
7. **Geisinger Health**, [name]
8. **Cleveland Clinic Lerner College of Medicine of CWRU**, [name]
9. **Northwestern Medical Center**, [name]
10. **Ochsner Clinic Foundation, Ochsner Health System**, [name]

STUDY TEAM ROSTER OF MAJOR PERSONNEL

SITE/PERSON	KEY ROLE(S)	TELEPHONE NUMBER
Columbia University Medical Center		
E. [name], FACS [contact]	Principal Investigator	[contact]
[name], Ph.D. [name]/[contact]/	Co-PI	917-
[name].	Neuropsych/Co-I	[name]

1 STUDY OBJECTIVES

1.1 Primary Objective

The purpose of this study is to evaluate the safety, feasibility and outcome of administering three different statins at submaximal and maximal dose on eCD and dCD. We hypothesize that a pre-operative statin regimen is protective against eCD (12-25h post-CEA) and dCD (30d), and early (365d) mortality. In addition, maximal doses may be essential in achieving optimal neuroprotection against eCD and dCD, with statins that pass the blood-brain barrier achieving similar effects at lower doses due to enhanced entry into the brain. In order to test this, our primary objectives will be:

- 1) Determine whether patients on a pre-existing sub-maximal dose of one of three most commonly prescribed statins (simvastatin <40mg, atorvastatin <80mg, rosuvastatin <20mg) experience a higher incidence of eCD and dCD than those randomized to 218 doses of pre-operative statin supplementation to the maximal FDA approved dose (simvastatin 40 mg, atorvastatin 80 mg, rosuvastatin 20 mg).
- 2) Determine whether approximately 2-18 doses of maximal statin supplementation is sufficient by comparing whether patients randomized to receiving statin supplementation each individually experience a higher incidence of eCD and dCD than those patients on a pre-existing maximal dose of the three most common statins, and whether statins that pass the blood-brain barrier better correlate with reduced eCD and dCD.
- 3) Determine whether patients on no pre-existing statin regimen exhibit less eCD and dCD when randomized to 2-18 doses of pre-operative maximal dose of atorvastatin (80mg) compared to lower dose of atorvastatin (10mg).
- 4) Determine a dose-response relationship to these 3 statins by determining whether all patients at the time of surgery have less eCD and dCD if they are on: 1) simvastatin 40mg rather than on <40mg; 2) atorvastatin 80mg rather than on <80mg; and 3) rosuvastatin 20mg rather than on <20mg.

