4.2 Exclusion Criteria

- 1) Patient has underlying disease other than atherosclerosis (i.e. autoimmune disease, known active malignancy).

- 2) Patient has documented dementia or screens out based on abnormal Baseline MoCA (≤ 25) and AD8 (≥ 2).
- 3) Patient's life expectancy is < 12 months.
- 4) Patient has advanced renal failure (serum creatinine > 2.5 mg/dL)
- 5) Patient has evidence of severe congestive heart failure or has history of end-stage cardiovascular disease (e.g. CHF NYHA Class III or IV or unstable angina).
- 6) Patient has history of intolerance or allergic reaction to any statins (myotoxicity, hepatic dysfunction, rash, etc.) – unless they would be in the Observational Arm (Arm 1) and therefore will not be receiving any study drug.
- 7) Patient has received an investigational drug within 30 days.
- 8) Patient is pregnant or lactating.
- 9) Except those eligible for the Observational Arm who do not receive any study statin, patient who is currently taking any of the following which have been shown to interact with atorvastatin and/or simvastatin and/or rosuvastatin (as per current drug package inserts):
 - *Cyclosporine;
 - *HIV Protease Inhibitors/Antivirals (e.g. roatanavir or plus roatanavir, tipranavir, lopinavir, boceprevir, saquinavir, darunavir, fosamprenavir, nelfinavir, efavirenz/tenofobir, atazanavir, simeprevir);
 - *Hep C Protease Inhibitor/Antivirals (e.g. telaprevir);
 - *Antibiotics (i.e. cobicistat-containing products like Tybost, rifampin/rifampicin, clarithromycin, telithromycin, erythromycin);
 - *Anti-fungals (i.e. itraconazole, ketoconazole, posaconazole, voriconazole, fluconazole); *Gemfibrozil; Other Fenofibrates (e.g. Tricor, fibric acid);
 - *Niacin > 1 g/day or statins in combination with niacin (e.g. Vytorin, Simcor);
 - *Colchicine;
 - *Danazol;
 - *Calcium Channel Blockers: Diltiazem, Varapamil;
 - * Dronedarone;
 - *Amiodarone;
 - *Digoxin;
 - *Ranolazine;
 - *Nefazodone;
 - *Warfarin/Coumadin;
 - *Lomitapide;
 - *Grapefruit juice (subject must be willing to avoid grapefruit juice).

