9.2 Sample Size and Randomization

Power Analysis

All of the aims will use logistic regression with presence of eCD as the response variable as the primary statistical analysis. A separate independent analysis for dCD will also be performed. Power calculations used data simulations (1000 simulations for each) with power=0.8, $\alpha=0.05$, and expected rates of eCD

based on existing preliminary data. For the comparison between subjects in arm 1 with a maximal dose (N=225) and those in arm 2 beginning with a sub-maximal dose and increasing to a maximal dose (N=338), the estimated minimum detectable effect size corresponds to a 65% reduction in eCD in the former cohort vs. the latter. For the comparison in between subjects in arm 2 beginning with a sub-maximal dose and increasing to a maximal dose (N=338) and those staying at the sub-maximal dose (N=337), the estimated minimum detectable effect size corresponds to a 46.7% reduction in eCD in the former cohort vs. the latter. For the comparison between subjects in arm 3 with 80 mg of atorvastatin (N=50) and those with 10 mg of atorvastatin (N=338), the estimated minimum detectable effect size corresponds to a 91.3% reduction in eCD in the former cohort vs. the latter.

Rationale for Sample Sizes

As per the power analysis above, the 1000 targeted patient enrollment is reasonable considering the aims of this study. We anticipate approximately 350 patients will be scheduled for CEA per year from the six participating institutions (Columbia-Presbyterian, St. Luke's Roosevelt, Cornell University, Valley Hospital, Montefiore Medical Center, and Buffalo Medical Center). Approximately 80% are anticipated to be asymptomatic, leaving 280 per year.

Expecting an approximate 75% recruitment rate, 210 eligible asymptomatic patients will be enrolled each year from the six sites. Over five years, this rate allows for 1000±50 patients to be enrolled. Based on our previous R01 grant, we estimate that a) 225 patients will already be on a pre-existing maximal statin regimen of simvastatin, atorvastatin, or rosuvastatin, b) 675 patients will be on a sub-maximal statin regimen of simvastatin, atorvastatin, or rosuvastatin, and c) 100 patients will be on no pre-existing statin regimen.

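### Objective 2 asks whether 2-18 doses are sufficient, but the plan offers only a difference test, with no margin, against a non-randomised arm whose entry rules conflict

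*Combined protocol and SAP*

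**What the plan says.** - **Objective (1.1).** Objective 2 begins "Determine whether approximately 2-18 doses of maximal statin supplementation is sufficient by comparing whether patients randomized to receiving statin supplementation". Sufficiency is to be judged by whether supplemented patients "each individually experience a higher incidence of eCD and dCD than those patients on a pre-existing maximal dose of the three most common statins".
- **Analysis (9.2, repeated in 9.5).** "All of the aims will use logistic regression with presence of eCD as the response variable as the primary statistical analysis", with a separate analysis for dCD.
- **Power (9.2).** For Arm 1 (225) against the Arm 2 patients raised to maximal dose (338), "the estimated minimum detectable effect size corresponds to a 65% reduction in eCD in the former cohort vs. the latter", at power 0.8 and alpha 0.05. The eCD rates used are not reported.
- **Design (3).** Arm 1 is observational; randomisation applies only within Arms 2 and 3.
- **Entry (4.2).** Exclusion 6 (statin intolerance or allergy) applies "unless they would be in the Observational Arm (Arm 1) and therefore will not be receiving any study drug". Exclusion 9 (interacting drugs) opens with "Except those eligible for the Observational Arm who do not receive any study statin, patient who is currently taking any of the following".
- **Adjustment (9.1).** Regression adjusts for risk factors out of balance at p<0.10. The interpretation paragraph expects randomisation to balance age, diabetes and other factors.
- **Objective 4 (1.1).** "Determine a dose-response relationship to these 3 statins by determining whether all patients at the time of surgery have less eCD and dCD" at the maximal dose of each statin than below it.

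**The concern.** A finding that a short course is sufficient requires evidence that any deficit against long-term maximal dosing is smaller than some stated amount. A test for a difference cannot give that, because a non-significant result may reflect only limited precision. Nothing in sections 1.1, 9.1, 9.2, 9.4 or 9.5 says how small the deficit must be, or how the result will be turned into a conclusion.

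The contrast also lies outside the randomisation. A difference between the groups, or its absence, could come from who entered Arm 1. At stake is a primary objective whose answer could be wrong in either direction. Objective 4 has a related weakness, because it sorts all patients by dose at surgery and so mixes Arm 1 with the randomised arms.

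**Working it through.** **Inputs.** Group sizes 338 and 225, alpha 0.05, power 0.80 and the 65% reduction are from 9.2. Sidedness is not stated; two-sided is assumed. Expected eCD rates are not stated. The nearest figures, in section 2.1.5, are 11.0% in asymptomatic statin users, 3.0% on simvastatin and 16.0% on atorvastatin. All rates below are therefore assumptions.

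**Step 1: the plan's 65%.** Let p2 be the rate in Arm 2 maximal and p1 = 0.35 × p2 the rate in Arm 1. Power = Φ[(p2 − p1 − 1.96·SE0)/SE1], with SE0 pooled and SE1 unpooled.
- p2 = 9.0%, p1 = 3.15%: SE0 = 0.02146, SE1 = 0.01944; (0.0585 − 0.0421)/0.01944 = 0.85; power 80%.
- p2 = 11%, p1 = 3.85%: SE0 = 0.02353, SE1 = 0.02131; (0.0715 − 0.0461)/0.02131 = 1.19; power 88%.

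The 65% fits a rate near 9%, which lies inside the 3.0%-16.0% range. It is plausible, but cannot be confirmed or refuted without the rate.

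**Step 2: how often the test misses a real deficit.** For every pair of event counts, compute the likelihood-ratio statistic for two proportions and add up the binomial probabilities of the pairs where it is below 3.84.

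| Arm 2 maximal | Arm 1 | Non-significant |
|---|---|---|
| 8% | 5% | 71.1% |
| 9% | 6% | 74.5% |
| 10% | 5% | 40.4% |
| 11% | 5.5% | 35.5% |

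The Step 1 formula gives 42% and 38% for the last two rows. In both of those rows the true rate after short supplementation is double that in Arm 1.

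**Step 3: what margin the sample could support.** With equal true rates p, SE = √[p(1−p)(1/n1 + 1/338)]. The 95% half-width is 1.96·SE. The margin with 80% power (one-sided 0.025) is (1.96 + 0.84)·SE = 2.80·SE.

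| p | n1 | SE (points) | Half-width (points) | Margin (points) |
|---|---|---|---|---|
| 3% | 225 | 1.47 | 2.9 | 4.1 |
| 8% | 225 | 2.33 | 4.6 | 6.5 |
| 11% | 225 | 2.69 | 5.3 | 7.5 |
| 16% | 225 | 3.15 | 6.2 | 8.8 |
| 8% | 180 | 2.50 | 4.9 | 7.0 |
| 11% | 180 | 2.89 | 5.7 | 8.1 |

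The 180 is an assumption: 20% of Arm 1 leaving the comparison after restriction. The documents do not say how many would.

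**Step 4: who is in Arm 1.** Section 4.2 lets Arm 1 include patients with past statin intolerance and patients on the listed interacting drugs. Section 5.3.3 says subjects will be screened for, and asked not to take, the same drugs during the dosing period, with no Arm 1 exception; section 5.1 gives Arm 1 a dosing period too. Section 7.3 says patients with side effects at their current or a higher dose will not be enrolled, again with no exception. The Arm 1 population is therefore not fixed by the text.

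**Step 5: Objective 4.** Arm 1 patients count on the maximal-dose side, apart from those on simvastatin 20 mg with amlodipine. No stratification by arm is stated, so selection into Arm 1 is mixed with dose.

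**The case against.** The strongest reply is that no sentence equates a non-significant test with sufficiency. That is correct. A reader might infer that the plan commits to this rule, but the interpretation paragraph in 9.1 makes no equivalence claim between Arm 1 and Arm 2 maximal; it only expects both to do better than the sub-maximal group. The rule is an inference, drawn because failing to find a higher incidence is the only route from the stated test to the stated conclusion. The absence of any criterion stands on either reading.

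Three other stronger readings should be set aside:
- *Arm 1 is a sicker population.* No section gives comorbidity by arm or the number entering under the waivers, and 5.3.3 and 7.3 cast doubt on whether the waivers operate.
- *No adjustment is planned.* Section 9.1 does plan it, and the data to be kept include age, diabetes and all standing medications. The weakness is choosing covariates by a p<0.10 screen.
- *The trial was sized for a 65% effect.* The total of 1000 follows from expected recruitment; 65% is what the resulting arm sizes could detect.

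A practical objection also stands. A 6.5-point margin on an 8% rate would tolerate up to 14.5%, and a tighter margin would often end inconclusive. That favours the descriptive option. If 'each individually' means one comparison per statin, precision is poorer still: with assumed equal thirds (75 v 113) the detectable reduction is about 92% at an 11% rate.

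**Conclusion.** The point holds in this form: a primary objective asks a no-important-deficit question, and the plan gives a difference test with no criterion for answering it, in a contrast that randomisation does not protect. On the assumed rates, a non-significant result is likely when the supplemented group is 3 points worse (71% at 8% v 5%) and common when its rate is double (35% to 40%). The percentages rest on those rates, a two-sided test and the full 225 and 338 patients. The missing criterion and the conflicting entry rules do not depend on them. No direction of bias can be claimed, and no single margin is a property of the trial. The randomised comparison in Objective 1 is unaffected. The sponsor should make the change before unblinding.

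**What to change.** 1. **Criterion.** Conclude 'sufficient' only if the upper 95% limit of the adjusted risk difference (Arm 2 maximal minus Arm 1) is below a margin fixed before unblinding; otherwise report 'inconclusive'. Alternatively, label Objective 2 descriptive and report the estimate with its interval. In either case state the achievable precision as a range over plausible rates and Arm 1 sizes, as in Step 3. Say whether the comparison is pooled or per statin.
2. **Population and covariates.** For this comparison use only Arm 1 patients who meet exclusions 6 and 9 as applied to Arm 2. Adjust for a set named in advance (age, diabetes, statin type, center, baseline neuropsychometric scores) in place of the p<0.10 screen.
3. **Objective 4.** Present the randomised dose contrasts within Arms 2 and 3 as the main evidence, and the pooled all-patient comparison that includes Arm 1 as supportive and non-randomised.
4. **Reconcile** section 4.2 with 5.3.3 and 7.3 on whether the restrictions apply to Arm 1.

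**Cost.** Items 1 and 2 are analysis-plan wording and use data already collected. An unknown number of Arm 1 patients leave this one comparison, which widens its interval. Item 3 changes the emphasis of a primary objective, so the sponsor must agree to it. Item 4 is a protocol clarification. No new visits or patients are needed.
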